##### *4.2.3.2. Competing risk of death*

The primary outcome – ICU LOS – is subject to the competing risk of death. Therefore, the ICU LOS represents a composite summary of two process: time to ICU discharge alive and time to ICU death. There are alternatives to deal with this scenario, such as 1) fitting competing risk models, modeling time to discharge alive and consider time to ICU death as a competing event, 2) analyzing LOS separately between ICU survivors and

non-survivors, 3) weighting differently the LOS for those who died, among others. As expected, the potential different results on the primary outcome analysis will likely occur or be relevant only if the intervention has an effect on mortality. We consider this a secondary analysis because, *a priori*, we did not expect a major impact of the intervention on mortality. In this sensitivity analysis, we will use the competing risk framework, presenting the analysis with cause-specific hazard ratios and sub-distribution hazard ratios for the time to discharge alive. The models will be adjusted for the same six covariates as the primary analysis, and the baseline period will be accounted as the mean ICU LOS at the unit level in the baseline period. We will account for the correlated data structure with a “shared frailty model”.

#### 4.2.4. Analysis of secondary outcomes at ICU level

The main outcome at the ICU level is the ICU performance classification. The performance will be defined in the baseline and after intervention periods without considering if the unit is in the intervention or control group. Thus, we will estimate if there will be a shift towards better performance for the ICUs in the intervention group, i.e., if there will be more commonly “most efficient” and “overachieving” ICUs in the intervention group.

Based on the background that the intervention might be more efficient overtime, in an exploratory analysis we will analyze the ICU performance classification at the last 3 months of the intervention.

For the ICU level outcomes, we will include all patients who fulfilled all inclusion criteria and none exclusion criteria, and we will include readmissions.

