## 2.4. Randomization and masking

After a 2-month observation period (baseline period) in which performance indicators for eligible ICUs were collected without any intervention (with the purpose of obtaining data for randomization, analysis and characterization of the initial ICU status), the ICUs eligible for the study were randomized. The 30 ICUs were randomly assigned to either the intervention group (n=15) or the control group (n=15) using a restricted randomization algorithm that minimizes imbalance between treatment groups across the following baseline covariates at the ICU level:

- 1) number of ICU beds

- 2) mean SAPS 3, in points
- 3) mean ICU length of stay (LOS), in days
- 4) Standardized mortality rate (SMR)
- 5) Standardized resource use (SRU), and
- 6) A two-category dummy indicator for Brazilian region where the ICU is located (regions South and Southeast x regions North/Northeast/Central-West).

We followed all the steps recommended by Carter and Hood during the application of the minimization algorithm. The randomization was performed at three times, including 14 units during the first randomization, followed by 7 and 9 units (Figure 1). We decided a priori to randomize at three times and the number of units at each randomization was pragmatic, allowing for ethical approval and completion of the baseline period, respecting the minimum of eight units during first randomization and minimum of six on subsequent randomizations.

For the first randomization, we followed the steps: 1) the database with the baseline data (2 months) were locked, 2) derivation of the six covariates per unit, 3) run the algorithm, generating the potential combinations of unit's allocation, 4) a random combination of allocations was selected. The order of each unit in the database was randomly sorted before the algorithm, as well as the order of potential allocations. The select allocation was coded as 0 and 1 by the algorithm. To select whether intervention would be 0 or 1, we performed the final simple randomization and 0 was allocated to the intervention arm. For the second and third blocks, we followed the same steps: we entered the baseline data of the previous block with its allocation and the new covariates. The algorithm accounts for the previous block covariates to calculate the new balance between

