### 2.5.2. Secondary exploratory outcomes

The secondary outcomes of this study include assessing the impact of interventions implemented through Telemedicine compared with a control group in the following outcomes:

At the unit level:

- Classification of the unit according to the profiles defined by the SRU and the SMR. The SRU reflects the observed / expected rate of resources used (estimated as ICU length of stay for surviving patients), adjusted by the patient's severity of illness (SAPS 3).

The SMR reflects the observed / expected rate (according to severity score) of hospital deaths. The profiles are a combination of SMR (above or below median) and SRU (above or below median): Each unit can be assigned to one of the four groups:

"most efficient" (SMR and SRU < median); "least efficient" (SMR, SRU > median);

"overachieving" (low SMR, high SRU), "underachieving" (high SMR, low SRU).

At an individual level:

- In-hospital mortality, defined as death by any cause, within the period from the date of ICU admission to the date of hospital discharge or death, whichever comes first.
- Incidence of central line-associated bloodstream infection (CLABSI), as defined by the CDC.
- Incidence of ventilator-associated event (VAE), as defined by the CDC.
- Incidence of catheter-associated urinary tract infection (CAUTI), as defined by the CDC.
- Ventilator-free days at 28 days, defined as the number of days from successfully weaning to day 28; patients who died before weaning were deemed to have no ventilator-free days
- Rate of patients receiving oral or enteral feeding, defined as any amount of oral or enteral diet, during ICU stay
- Rate of patients under light sedation or alert and calm [Richmond Agitation-Sedation Scale (RASS) = -3 to +1]
- Rate of patients under normoxemia [peripheral oxygen saturation (SpO2) between 92% and 96%]

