#### 4.1.4. Multiplicity

Pre-specified secondary outcomes and subgroup analyses will not be adjusted for multiple comparisons. They should, therefore, be interpreted as exploratory.

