### 5.1.6. Times series of ICU LOS, SMR and SRU

We will present times series of ICU LOS, SMR, and SRU from baseline, aggregating the 2 months, and then aggregating every 3 months for the treatment and control group. In a supplementary figure, we will replicate it for each ICU.

We will present an alluvial plot with all 30 ICUs ICU performance categorized in 4 categories, with the time axis as of the times series.

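### The main ICU-level contrast reduces to SMR below a median pooled over both arms: it ignores SRU, its counts are tied between the arms, and it has less power than a continuous comparison.

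*SAP*

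**What the plan says.** Section 4.2.4 ranks the outcome: "The main outcome at the ICU level is the ICU performance classification". Section 2.5.2 defines the classes: "The profiles are a combination of SMR (above or below median) and SRU (above or below median". *Most efficient* is low on both ratios, and *overachieving* is "low SMR, high SRU".

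Section 4.2.4 says how the classes are formed, "The performance will be defined in the baseline and after intervention periods without considering if the unit is in the intervention or control group", and what they are for: "we will estimate if there will be a shift towards better performance for the ICUs in the intervention group". It describes that shift as more *most efficient* and *overachieving* ICUs in the intervention arm. It names no test, model or effect measure, and it does not say whether the medians are carried forward from baseline or recomputed. The same classification is repeated for the last 3 months as an exploratory analysis.

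Section 2.4 gives the numbers: "The 30 ICUs were randomly assigned to either the intervention group (n=15) or the control group (n=15". Section 5.1.6 plots continuous SMR and SRU over time by arm, without a stated comparison, and adds: "We will present an alluvial plot with all 30 ICUs ICU performance categorized in 4 categories". Section 4.1.4 sets the status: "Pre-specified secondary outcomes and subgroup analyses will not be adjusted for multiple comparisons", so the result is to be read as exploratory.

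**The concern.** Three features of this outcome work against its purpose.

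- The better pair covers both levels of SRU, so SRU drops out. SRU is the ratio built on length of stay in survivors, which is the domain of the primary hypothesis. SMR is built on hospital deaths, where section 4.2.3.2 expects no major effect.
- With medians pooled over arms and recomputed in each period, class membership is a rank among the 30 ICUs. A control ICU whose SMR has not moved can be shown as having become worse. An improvement or deterioration shared by both arms disappears. Section 4.1.5 says that the trial ran through the COVID-19 pandemic, so a shared change is plausible.
- Cutting a continuous ratio in two, with only 30 units, costs power.

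At stake are the reading of the class table and alluvial plot, and the chance that the main ICU-level analysis detects a real change.

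**Working it through.** **1. The plan's own figure.** The SAP states no power for the ICU-level outcome. Its 80% in section 2.6.1 is for ICU length of stay, and it reproduces:
- Design effect = 1 + (500 − 1) × 0.018 = 9.98.
- Effective size per arm = 15 × 500 / 9.98 = 751.
- SE = 10 × √(2/751) = 0.516 days, and 1.5/0.516 = 2.91.
- Power from the noncentral t with 28 df = 80.1% (79.3% with a cluster-size CV of 0.15).

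This gives no input for SMR or SRU.

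**2. What the better pair is.**

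| | SRU below median | SRU above median |
|---|---|---|
| SMR below median | most efficient (better) | overachieving (better) |
| SMR above median | underachieving | least efficient |

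The two better cells are the whole top row, so the contrast is low SMR against high SMR.

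**3. Tied counts.** Let a and c be the numbers of low-SMR ICUs in the intervention and control arms. With a recomputed pooled median, a + c = 15, so a − c = 2a − 15. The contrast is twice the departure of either arm from 7.5. In simulation with log SMR lower by 0.2 in the intervention arm and no control ICU changed (other inputs as in step 6), the mean counts were 9.8 and 5.2. The difference is 4.6 = 2 × 2.3. With medians fixed at baseline, this constraint would not apply after randomization.

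**4. An exact test on the split (test assumed).** 10 against 5 gives p = 0.14, and 11 against 4 gives p = 0.027. Rejection therefore needs 11 against 4 or more extreme, and the true size is 2.7%.

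**5. Power in SD units.** The inputs are assumed: 40,000 simulated trials of 15 + 15 ICUs, normal ICU-level values, two-sided 5%, effect d on SMR in SDs between ICUs.

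| d | t-test on SMR | Median split | Relative loss |
|---|---|---|---|
| 0.50 | 26.3% | 13.0% | 1 − 13.0/26.3 = 51% |
| 0.75 | 50.9% | 27.6% | 1 − 27.6/50.9 = 46% |
| 1.06 | 79.9% | 52.7% | 1 − 52.7/79.9 = 34% |

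The next table uses a continuous analysis adjusted for the ICU's own baseline value, with the effect set so that this analysis has 80% power. Half of that power is 40%.

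| Baseline correlation | Split, unadjusted | Split, adjusted for baseline class |
|---|---|---|
| 0 | 55% | 57% |
| 0.5 | 42% | 53% |
| 0.6 | 37% | 50% |
| 0.7 | 29% | 45% |
| 0.8 | 21% | 37% |

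The loss passes one half above a correlation of about 0.5, or about 0.75 if the split is also adjusted.

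**6. The same on the SMR scale.** Assume a between-ICU SD of log SMR of 0.25 and a sampling SD of 0.20 at baseline and 0.07 later. An effect of −0.2 is exp(−0.2) = 0.82, an 18% lower SMR. The later SD is √(0.25² + 0.07²) = 0.26, so d = 0.2/0.26 = 0.77. Power is about 29–30% for the split and 52–54% for continuous log SMR. With baseline adjustment it is 53–71% for true correlations of 0.3 to 0.8. Like for like the loss is 1 − 29/53 = 45%. If the exact test is randomised to a true size of 5%, the split has 35%, a loss of 1 − 35/53 = 34%.

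**7. Effect on SRU only (d = 1.06).** A t-test on SRU has 80% power. The low-SMR contrast rejects in 2.7% of trials, its null rate. A chi-square test on all four classes would recover 41–45%, but section 4.2.4 does not name one.

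**The case against.** The strongest reply is that this is an exploratory outcome taken from a published profile method in which relative ranking is intended. What stands of the more specific objections:

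- *The split discards more than half of the power.* A reader might infer this, but the documents do not support it as a general statement. They give no SD, effect or correlation for SMR. Like for like, the loss is about one third where the t-test has 80% power, and part of it comes from the conservative exact test, which the SAP does not prescribe. For normal data a median split has an asymptotic efficiency of 2/π, about 64%.
- *Tied counts bias the comparison.* They do not. The null rejection rate is 2.7%, so type I error is not inflated. The question asked is between arms, and the tie affects only the reading of change within an arm.
- *The medians are redrawn in each period.* Section 4.2.4 does not say so outright. It is the natural reading of a class defined in both periods, but it remains a reading.
- *Baseline is ignored.* Section 4.2.4 looks for a shift between periods, and section 4.2.6 lists baseline performance class among the covariates for primary and secondary outcomes. What is not used is the ICU's continuous baseline value.
- *The information is shown elsewhere.* Section 5.1.6 plots SMR and SRU by arm and by ICU, and mortality and length of stay are modelled at patient level. This softens the harm, but it gives no ICU-level estimate with a confidence interval.

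None of this answers the point that the better pair leaves out SRU.

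**Conclusion.** The point holds in a limited form. Two parts follow from the definitions alone: the named contrast is SMR below the median and so excludes SRU, and with recomputed medians the low-SMR counts sum to 15 over the arms (barring ties). Within-arm change then cannot be read from the classes, and a common change cannot appear.

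The power loss rests on assumed values. It is about one third to one half against a like-for-like continuous comparison. It is more than half only against an analysis adjusted for a strongly correlated baseline. For an effect on SRU alone, the named contrast has essentially no power beyond its null rate. The between-arm test remains valid. Because the outcome is exploratory, this should be changed but does not threaten the trial's primary conclusion.

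**What to change.** Add to section 4.2.4, as the inferential ICU-level comparison, two linear regressions across the 30 ICUs: post-randomization log(SMR) on arm and the ICU's own baseline log(SMR), and the same for log(SRU). Report each arm effect as a ratio with 95% CI. Use the same models for the last 3 months.

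Keep the pre-specified four-class table and the alluvial plot as description. State whether the medians are fixed at baseline or recomputed in each period. If recomputed, note beside the table and plot that the counts below each median sum to 15 over the two arms.

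The cost is SAP wording and two small models on quantities already derived for randomization (section 2.4) and for the time series (section 5.1.6). The price is that the class shift becomes descriptive. The outcome stays exploratory. Section 1 says that no analysis has yet been undertaken, so the change can still be made before database lock.

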#### 4.2.5. Analyses of secondary outcomes at patient level

For all secondary outcomes at the individual level, we will fit the Equation (1) using generalized linear mixed models to accommodate each secondary outcome (e.g., logistic mixed model for mortality; Poisson/negative-binomial for rates, etc.). We will adjust for the same covariates, except when it is not possible because of the outcome type. For instance, ventilator associated events can be measured only in patients with invasive mechanical ventilation.

For the secondary outcomes that involve rates or patient-days, catheter-days and etc., we will include all patients who fulfilled all inclusion criteria and none exclusion criteria, and we will include readmissions.

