#### 4.2.6. Covariate adjustment

We pre-specified that the analyses for the primary and secondary outcomes will be adjusted by covariates in the original protocol, but we did not define which covariates, except the mean ICU LOS at the cluster level. Based on the literature on the determinants of ICU LOS, we will adjust by three patient level covariates and four ICU level covariates:

- 1) SAPS-3 (continuous term),
- 2) Type of ICU admission (3 categories: medical, elective surgical, unplanned surgical),
- 3) Invasive mechanical ventilation at ICU admission (2 categories: yes, no),
- 4) Number of ICU beds in the baseline (continuous term),

- 5) Brazilian region where the ICU is located (2 categories: South/Southeast, North/Northeast/Central-West),
- 6) ICU performance in the baseline (4 categories: most efficient, least efficient, overachieving, underachieving).
- 7) Groups of randomization (3 categories: first, second and third blocks)

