5.1.4. Table with the effect estimates of the intervention

	Intervention ICUS		Control ICUs				
	Baseline period	Intervention period	Baseline period	Intervention period	Effect estimate type	Adjusted Effect estimate (95% CI)	P Value
Primary outcome							
Number of patients	N	N	N	N			
ICU LOS, days	mean (SD)	mean (SD)	mean (SD)	mean (SD)	AAA	X.XX (X.XX to X.XX)	0.XXX
Sensitivity analyses of primary outcome definition							
Readiness for discharge	mean (SD)	mean (SD)	mean (SD)	mean (SD)	AAA	X.XX (X.XX to X.XX)	0.XXX
Sensitivity analysis for the competing risk of death					AAA	X.XX (X.XX to X.XX)	0.XXX
Secondary outcomes							
Number of patients	N	N	N	N	AAA	X.XX (X.XX to X.XX)	0.XXX
Secondary Outcome Y	Z	Z	Z	Z	AAA	X.XX (X.XX to X.XX)	0.XXX
...	...	...	...	...	...	...	...

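### The written contrast for the ICU-level performance outcome (more most-efficient and overachieving ICUs) is exactly SMR below the median, so it cannot register an SRU-only gain

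*SAP*

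**What the plan says.** SAP section 2.5.2 crosses two median splits, on SMR and on SRU. Low on both is *most efficient* and high on both is *least efficient*. The mixed classes are given as "overachieving' (low SMR, high SRU), 'underachieving' (high SMR, low SRU". On the resource axis, "The SRU reflects the observed / expected rate of resources used (estimated as ICU length of stay for surviving patients", adjusted for SAPS 3. SMR is observed over expected hospital deaths.

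Section 4.2.4 calls the classification the main outcome at ICU level. Classes are assigned at baseline and after randomisation, "without considering if the unit is in the intervention or control group". The analysis is to look for a shift towards better performance, which the section then spells out as "more commonly “most efficient” and “overachieving” ICUs in the intervention group". It gives no order for the four classes, no model and no separate contrast for SRU.

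Three other places bear on this:
- Section 4.2.6: "We pre-specified that the analyses for the primary and secondary outcomes will be adjusted by covariates in the original protocol". The listed covariates include baseline performance class and randomisation block.
- Section 5.1.4: the results table has a column headed "Adjusted Effect estimate (95% CI") for secondary outcomes.
- Section 5.1.6: "We will present times series of ICU LOS, SMR, and SRU from baseline", by arm, together with an alluvial plot of the four classes.

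Sections 2.5.2 and 4.1.4 make the secondary outcomes exploratory, without multiplicity adjustment.

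**The concern.** The outcome is built from two axes, but the only direction of benefit written for it uses one. The unused axis is the one closest to the trial's aim: section 1 states that the intervention is meant to reduce ICU length of stay, and SRU is derived from length of stay in survivors. The axis that is used is mortality, where section 4.2.3.2 says no major effect was expected.

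If the intervention shortened severity-adjusted stay and left mortality unchanged, the rule as written would therefore report no shift in ICU performance. At stake is the reading of one exploratory outcome, not the trial's main conclusion.

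**Working it through.** The SAP gives no sample size or power for this outcome, so there is no figure to reproduce. The main check is logical. The simulations only illustrate it.

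**1. The definitions laid out (section 2.5.2), with the classes counted as better (section 4.2.4)**

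| | SRU low | SRU high |
|---|---|---|
| SMR low | most efficient: counted | overachieving: counted |
| SMR high | underachieving: not counted | least efficient: not counted |

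The counted cells are the whole top row:

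{SMR low, SRU low} ∪ {SMR low, SRU high} = {SMR low}.

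**2. What an SRU-only gain does.** It moves an ICU from right to left within its row:
- overachieving → most efficient: counted before and after;
- least efficient → underachieving: not counted before or after.

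The combined count does not change. If the two classes are read separately instead, the first move makes *most efficient* commoner and *overachieving* rarer, so they cannot both become commoner through an SRU gain.

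**3. Expected counts.** Inputs: 15 ICUs per arm (section 2.4); medians taken over all 30 ICUs, which is how the arm-blind classification is read here; SMR and SRU as unit normals (assumed); 8,000 runs per scenario. Mean number of ICUs, intervention vs control:

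| Effect in intervention ICUs | most efficient | overachieving | combined |
|---|---|---|---|
| SRU 1 SD lower, SMR unchanged | 5.2 vs 2.3 | 2.3 vs 5.2 | 7.5 vs 7.5 |
| SRU 2 SD lower, SMR unchanged | 6.3 vs 1.2 | 1.2 vs 6.4 | 7.5 vs 7.5 |
| SMR 1 SD lower, SRU unchanged | 5.2 vs 2.3 | 5.2 vs 2.3 | 10.4 vs 4.6 |
| SMR and SRU both 1 SD lower | 7.2 vs 1.4 | 3.2 vs 3.2 | 10.4 vs 4.6 |

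Adding an SRU effect to an SMR effect leaves the combined count at 10.4 vs 4.6.

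**4. Does the planned covariate adjustment help?** Inputs: SRU ratio 6.5/8.0 = 0.8125, from the length-of-stay means in section 2.6.1. Those means are for all patients while SRU uses survivors, so 0.90 was run as well. Assumed, because the SAP gives none of them: SD of log SRU 0.3 or 0.4; SD of log SMR 0.25; baseline-to-post correlation 0.5, 0.7 or 0.82; SMR–SRU correlation 0, 0.3 or 0.6; arm splits of 4/3 and 4/5 in blocks 2 and 3. A linear model of the combined class on arm, four-category baseline class and block gave an arm effect of −0.8 to +0.6 percentage points and rejected in 4–6% of runs, which is the null rate. Adjustment does not change what is counted.

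**5. What would respond to SRU, under the same assumptions.** The model for the direct alternative is

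log SRU(post) = a + b·arm + c·log SRU(baseline) + block, with 30 − 5 = 25 df and ratio = exp(b).

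| Analysis, adjusted for baseline and block | Rejection at SRU ratio 0.81 |
|---|---|
| Combined two classes | about 5% |
| Four classes scored, SMR first | about 7–12% |
| Four classes scored, SMR and SRU weighted equally | about 10–20% |
| log SRU regression | 32–88% |

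At ratio 0.90 the log SRU regression has 12–36% power.

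**The case against.** The strongest defence is that ranking ICUs by mortality first is a legitimate choice. Length of stay is already the primary outcome, and naming the two low-SMR classes amounts to stating that choice. This stands in part: the contrast is not wrong as an SMR contrast. But the SAP presents it as the meaning of better performance on a two-axis outcome and nowhere says that SRU is left out.

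A second defence is that the word shift implies an ordinal analysis. An ordered analysis would respond to SRU, but no order is written, and the relative rank of *overachieving* and *underachieving* is left open.

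A third is that close relatives of SRU and SMR are already modelled: length of stay adjusted for SAPS 3 (sections 4.2.1 and 4.2.6), time to discharge alive (4.2.3.2) and the "logistic mixed model for mortality" (4.2.5). This is correct and limits what is lost. A reader might infer that the trial would have no between-arm evidence on severity-adjusted stay. The documents do not support that.

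A reader might also infer that the figures in section 5.1.6 are the sole source of SRU information by arm. That goes too far: class frequencies by arm and period could appear in the table of section 5.1.4, and the low-SRU share could be read from them. Both sources would be descriptive for SRU.

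**Conclusion.** The point holds as a cheap improvement to an exploratory outcome. By the SAP's own definitions, the one contrast written for ICU performance is a split on SMR alone and cannot detect an SRU-only gain. That conclusion follows from the class definitions and needs no assumption about effect size, SD, correlation or how the medians are taken.

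The percentages are illustrative, because they rest on SDs, correlations and block splits that the SAP does not give. A reader might take them to show that an SRU regression would be well powered. They do not: over the assumed range it runs from weak to good at ratio 0.81 and stays low at 0.90. They show only that it responds to SRU where the combined count does not.

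Nothing here touches the primary analysis, its sensitivity analyses or the patient-level mortality model.

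**What to change.** In section 4.2.4:
1. Keep the four-class classification as the ICU-level outcome, with its alluvial plot.
2. Either label the combined two-class contrast as SMR-only, or state an order of the four classes in which lower SRU counts as better.
3. Add an exploratory ICU-level comparison of post-randomisation log SRU between arms, adjusted for baseline log SRU and randomisation block, reported as a ratio with 95% CI. The same for log SMR is optional, given the mortality model already planned.

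The cost is one or two sentences and one or two small regressions on 30 ICUs, using quantities that section 5.1.6 already requires. Section 1 states that no analysis has been undertaken, so the change can be dated before database lock. The downside is one or two more exploratory estimates without multiplicity control, with power that may be modest. If only step 2 is done, the wording is repaired, but there is still no direct estimate of the SRU difference.
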